12.1.4 Dose reductions

All dose reductions should be considered and described, specifying the reason for reduction (drug related, non-drug related or other causes).

Listing 12.1.4.1 Dose reductions

Patient id.	Cycle	Day	Cycle start date	Previous dose	Reduced dose	Reason for dose reduction	Dose reduction Spec.

Table 12.1.4.2 Number of patients and cycles with dose reduction, any relationship

	N	%
No. of patients treated	X	X.X
No. of patients susceptible to have a dose reduced*		
No. of patients with any dose reduced**		
No. of patients with**:		
No plitidepsin reduction		
1 cycle with plitidepsin dose reduced		
2 cycles with plitidepsin dose reduced		
No. of cycles administered		
No. of cycles susceptible to have any dose reduced***		
No. of cycles with plitidepsin dose reduced ****		
No. of cycles with plitidepsin dose reduced (Treatment-related)		

(*) All patients with more than one infusion. (**) Denominator = Number of patients susceptible to have a dose reduced

(***) All cycles excluding first cycle of those patients who have only received the first infusion. (****) Denominator= Number of cycles susceptible to have a dose omission

NA: Not applicable

Table 12.1.4.3 Number of patients and cycles with dose reduction according to the relationship

Reasons for reductions	N	%
No. of cycles with dose reductions*		
Treatment-related	X	X.X
Non-treatment-related		

(* Denominator= Number of cycles susceptible to have a dose omission

NA: Not applicable

Listing 12.1.4.4 Dose reductions due to AEs

Patient id.	Cycle	Preferred term code	Adverse event reported (verbatim)	Grade	Relationship	Onset date	Resolved date	Significant consequences

AEs with action = 'Dose reduced/adjusted' or 'Reduced and delayed'.

12.1.5 Infusions temporarily interrupted

A listing of the patients who had infusions temporarily interrupted with the corresponding reasons will be provided.

Listing 12.1.5.1 Interrupted Infusions listing.

Patient id.	Cycle	Infusion	Interrupted	Reason
			Yes	

12.1.6 Prophylactic medication administration

A listing of the patients who have not received Ondansetron, Diphenhydramine and Ranitidine or equivalents with the corresponding reasons will be reported.

Listing 12.1.6.1 Patients and cycles without prophylactic medication administration

Patient id.	Cycle	Infusion	Prophylactic medication not taken*	Reason
...				

(* Ondansetron, diphenhydramine or ranitidine.

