## 7.3 PROPHYLACTIC MEDICATION

All patients must receive the following prophylactic medication 30–60 min before infusion of plitidepsin:

- 1) Dexamethasone (8 mg i.v. or equivalent)
- 2) 5-HT3 receptor antagonist: palonosetron 0.25 mg i.v. or tropisetron 5 mg i.v. or granisetron 3 mg i.v. (avoid ondansetron as this drug is categorized within a known risk of producing Torsade de Pointes) (see [Appendix 8](#)). Alternatively, metoclopramide or other antiemetic drugs may be used instead as per Investigator's criteria/institutional guidelines, and
- 3) Diphenhydramine hydrochloride 25 mg i.v. or equivalent, and
- 4) Ranitidine 50 mg i.v. or equivalent.

Oral metoclopramide and/or extended oral 5-HT3 receptor antagonist may be used as per Investigator's criteria/institutional guidelines. Additional dexamethasone can only be used as an antiemetic in the event alternative antiemetics cannot be used; and only if the Investigator considers the options above as insufficient.

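### SAP Listing 12.1.6.1 omits dexamethasone, which Protocol 7.3 makes mandatory, and names ondansetron, which Protocol 7.6.2 prohibits, as its antiemetic

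*SAP*

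**What the plan says.** Protocol 7.3, with the same content in the Synopsis, opens with "All patients must receive the following prophylactic medication" and gives four numbered components, to be taken 30 to 60 minutes before plitidepsin:

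1. "Dexamethasone (8 mg i.v. or equivalent").
2. A 5-HT3 antagonist, "palonosetron 0.25 mg i.v. or tropisetron 5 mg i.v. or granisetron 3 mg i.v", with the instruction to "avoid ondansetron as this drug is categorized within a known risk of producing Torsade de Pointes". The same item then widens the choice: "Alternatively, metoclopramide or other antiemetic drugs may be used instead as per" the investigator's criteria or institutional guidelines.
3. "Diphenhydramine hydrochloride 25 mg i.v. or equivalent".
4. Ranitidine 50 mg i.v., or an equivalent.

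Protocol 7.6.2, item 5, and the matching Synopsis entry prohibit any drug with a known risk of Torsade de Pointes and name ondansetron. Appendix 8 puts ondansetron on risk list 1, the known-risk list.

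SAP Appendix I, section 12.1.6, defines the corresponding output as "A listing of the patients who have not received Ondansetron, Diphenhydramine and Ranitidine or equivalents", with reasons. The footnote to Listing 12.1.6.1 explains the column for medication not taken as "Ondansetron, diphenhydramine or ranitidine".

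**The concern.** A programmer builds the listing from the SAP, not from the protocol. Built as specified, it has two faults.

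- **Dexamethasone is not checked.** It is the first mandatory component, but it is in neither the sentence nor the footnote. The listing's title refers to prophylactic medication in general, so an empty listing would be read as full compliance even if some infusions had been given without the steroid.
- **The named antiemetic is one the protocol forbids.** A patient given ondansetron counts as having had the antiemetic, although the protocol excludes that drug because of its arrhythmia risk. QT safety is prominent in this trial: there are QT exclusion criteria, a rule to discontinue at QTc grade 2 or higher, and ECGs around the Cycle 1 infusions.

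What is at stake is the accuracy of a compliance listing in the safety section.

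**Working it through.** There is no figure in the plan to reproduce and no formula to apply. The check sets the two documents side by side and then runs simple cases through the SAP wording.

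**Component by component**

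| Protocol 7.3 component | SAP 12.1.6 sentence | Footnote to Listing 12.1.6.1 |
|---|---|---|
| 1. Dexamethasone or equivalent | Not named | Not named |
| 2. Palonosetron, tropisetron or granisetron, or another antiemetic; ondansetron to be avoided | Ondansetron, equivalents allowed | Ondansetron, no allowance for equivalents |
| 3. Diphenhydramine or equivalent | Named, equivalents allowed | Named, no allowance for equivalents |
| 4. Ranitidine or equivalent | Named, equivalents allowed | Named, no allowance for equivalents |

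The protocol requires 4 components and the SAP addresses 3, so 4 − 3 = 1 is absent: dexamethasone.

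**Can the allowance for equivalents bring dexamethasone in?** No. The protocol lists it as a separate numbered component with its own allowance for an equivalent. A corticosteroid is not a substitute for an antiemetic, diphenhydramine or ranitidine. The allowance can bring the permitted 5-HT3 antagonists into the SAP sentence, and that part of the sentence is workable.

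**Three cases.** The sentence joins the three drugs with 'and', so it could mean that any one is missing or that all three are. Both readings are tried, with equivalents allowed.

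- *Case A: only dexamethasone missed; a permitted antiemetic, diphenhydramine and ranitidine given.* Of the three checked components, none is missing. 'Any missing' is false and 'all missing' is false, so the infusion is not listed under either reading.
- *Case B: ondansetron given as the only antiemetic; the rest correct.* Again none of the three checked components is missing, so the infusion is not listed under either reading, although the patient had no permitted antiemetic.
- *Case C: fully compliant, with palonosetron.* Not listed under the sentence, which is correct. Under the footnote read literally, ondansetron was not taken, so if any one missing drug triggers a row this compliant infusion is listed.

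Case A under that literal footnote is also listed if the patient had, say, granisetron, but the row would report ondansetron as the drug not taken. It would look the same as Case C and would still say nothing about dexamethasone.

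**Other outputs that hold the information**

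- Listing 13.1.9 (prophylactic medication) and Listing 13.1.28 (concomitant medications) are raw database listings.
- SAP 8.4 covers deviations in concomitant medication, and Listing 10.3.1 lists protocol deviations by patient, type and description.
- None of these defines a check for missed dexamethasone. Listing 12.1.6.1 is the only SAP output specified to identify missed prophylaxis.

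**The case against.** The strongest reply is that little is lost. Protocol 5.2.2 treats any departure from the protocol as a deviation and requires detected deviations to be documented. An infusion without dexamethasone or an equivalent is such a departure, so it belongs in Listing 10.3.1 and ICH Listing 16.2.2, and the raw record is in Listing 13.1.9. This stands as mitigation. It does not make Listing 12.1.6.1 right: the deviation listings show only what has been detected and recorded as a deviation, whereas this listing is meant to find the missed doses from the data.

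On ondansetron, one can argue that the listing concerns prophylaxis not given, not prohibited drugs given. A patient on ondansetron did receive an antiemetic, prohibited use belongs with the deviations, and the SAP nowhere permits the drug. Much of this is fair: the ondansetron part is the weaker of the two, and its use is already reportable under SAP 8.4 and Listing 10.3.1. What remains is that the protocol's requirement is for an antiemetic other than ondansetron, so a compliance check should not accept ondansetron as meeting it. Listing such an infusion as lacking a permitted antiemetic and recording the ondansetron as a deviation are compatible, because they answer different questions.

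The names may simply have been carried over from another study's template. That would explain the error but would not change the output.

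**Conclusion.** The point holds and is minor. The listing specification is wrong as written: it leaves out 1 of the 4 mandatory components, and for another it names a drug the protocol prohibits. An infusion missing only dexamethasone goes unlisted whether the sentence means any drug missing or all three missing, provided the allowance for equivalents in the sentence is applied. If the footnote is instead taken literally, compliant infusions can be listed as well, and missed dexamethasone is still not identified.

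The consequence stops at this descriptive listing. The primary endpoint, the sample size, the error rates, the futility rules and the efficacy analyses do not use it. The documents give no frequency for missed dexamethasone or for ondansetron use, so the number of infusions affected cannot be estimated.

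**What to change.** Reword SAP 12.1.6 so that the listing shows each infusion for which any of the following was not given, with the reason:

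- dexamethasone or equivalent;
- palonosetron, tropisetron, granisetron or another permitted antiemetic, with ondansetron not counting;
- diphenhydramine or equivalent;
- ranitidine or equivalent.

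Make the footnote to Listing 12.1.6.1 name the same four components, with the same allowance for equivalents and the same exclusion of ondansetron. Keep the reporting of ondansetron use itself in Listing 10.3.1, as already planned.

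The cost is one sentence and one footnote. The source data are already planned in Listings 13.1.9 and 13.1.28, so no new data collection is indicated.

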12.2 Adverse Events (AEs)

12.2.1 Display of adverse events

Table 12.2.1.1 Summary of adverse events.

	N (%)
Patients with at least one AE regardless relationship	X (X.X)
Any treatment-related AE	
Any grade 3/4 AE	
Any grade 3/4 treatment-related AE	
Any SAE in DB	
Any treatment-related SAE	
Any grade 3/4 SAE	
Any grade 3/4 treatment-related SAE	
AEs leading to death	
AEs treatment-related leading to death	
AEs leading to dose delay	
AEs leading to dose reduction	
AEs leading to treatment discontinuation	
AEs treatment-related leading to treatment discontinuation	

Table 12.2.1.2 Evolution of lymphoma-related AEs at baseline

		Worst grade per patient						Total		
		0		1		...		N	%	
		N	%	N	%	N	%			
Baseline	Fatigue	Grade 0	X	X.X	X	X.X	X	X.X	X	X.X
		Grade 1								
									
	Bone Pain	Grade 0								
		Grade 1								
									
	Myopathy	Grade 0								
		Grade 1								
									

Table 12.2.1.3 Treatment-related* adverse events. Worst grade by patient

	Preferred Term	Grade 1		...	Grade 4		All**	
		N	%	...	N	%	N	%
SOC	Anemia NOS	X	X.X		X	X.X	X	X.X
Blood and lymphatic system disorders	...							
Cardiac disorders	Arrhythmia NOS							
	...							

(* or Unknown relationship (***) Any grade

Table 12.2.1.4 Treatment-related* adverse events. Worst grade by cycle

	Preferred Term	Grade 1		...	Grade 4		All**	
		N	%	...	N	%	N	%
SOC	Preferred Term	N	%	...	N	%	N	%
Blood and lymphatic system disorders	Anemia NOS	X	X.X		X	X.X	X	X.X
	...							
Cardiac disorders	Arrhythmia NOS							
	...							

(* or Unknown relationship (** Any grade

Table 12.2.1.5 Adverse Events regardless of relationship. Worst grade by patient

	Preferred Term	Grade 1		...	Grade 4		All*	
		N	%	...	N	%	N	%
SOC	Preferred Term	N	%	...	N	%	N	%
Blood and lymphatic system disorders	Anemia NOS	X	X.X		X	X.X	X	X.X
	...							
Cardiac disorders	Arrhythmia NOS							
	...							

(* Any grade

Table 12.2.1.6 Adverse Events regardless of relationship. Worst grade by cycle

	Preferred Term	Grade 1		...	Grade 4		All*	
		N	%	...	N	%	N	%
SOC	Preferred Term	N	%	...	N	%	N	%
Blood and lymphatic system disorders	Anemia NOS	X	X.X		X	X.X	X	X.X
	...							
Cardiac disorders	Arrhythmia NOS							
	...							

(* Any grade

Listing 12.2.1.7 Treatment-related* grade 3-4 adverse events. Worst grade by patient

Patient id.	SOC Name	Preferred term	Grade

(* or Unknown relationship

Listing 12.2.1.8 Treatment-related* grade 3-4 adverse events. Worst grade by cycle

Patient id.	Cycle	SOC Name	Preferred term	Grade

(* or Unknown relationship

Listing 12.2.1.9 Adverse Events grade 3-4 regardless of relationship. Worst grade by patient

Patient id.	SOC Name	Preferred term	Grade

Listing 12.2.1.10 Adverse Events grade 3-4 regardless of relationship. Worst grade by cycle

Patient id.	Cycle	SOC Name	Preferred term	Grade

At the time of the analysis, if appropriate, grouping of similar or clinically related items will be made.

12.3 Serious Adverse Events and deaths.

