### **8.5.3 Death**

Death as such is the outcome of a SAE and should not be used as the SAE term itself, whenever possible. The cause of death should be recorded as the SAE term instead. When available, the autopsy report will be provided by the Sponsor.

Grade 5 should be used only for events for which there is a causal relationship with the patient's death (e.g. the event was the direct cause of the death). Grade 4 should be used for the events with the outcome of death but there is no causal relationship between them (e.g. the death was not directly caused by the reported event but related to other comorbidities or complications).

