12.5.2 LVEF, ECG and other related tests

Listing 12.5.2.1 Electrocardiogram results. Evolution during the study.

Patient id.	Cycle	ECG result

Listing 12.5.2.2 LVEF evolution during the study.

Patient id.	LVEF(%)		
	Baseline*	Minimum*	End of treatment*
	X.X	X.X	X.X
Median(Range)	X.X (X.X-X.X)	X.X (X.X-X.X)	X.X (X.X-X.X)

(*) LVEF (%) value and method

Listing 12.5.2.3 Median change in LVEF.

Cycles	LVEF
Baseline	X.X (X.X-X.X)
Minimum	X.X (X.X-X.X)
End of treatment	X.X (X.X-X.X)

12.6 Concomitant therapy / procedures according to the ATC classification.

Table 12.6.1 Concomitant medication during treatment (ATC levels)

Medication Term (ATC level 1)	Medication Term (ATC level 2)	Medication Term (ATC level 4)	Preferred Name		
				N	%
				X	X.X

Listing 12.6.2 Patients with EPO or G-CSF.

Patient id.	Type	Route	Dose	Unit	Start date	Stop date	Reason	Indication

Listing 12.6.3 Patients with any transfusion during treatment

Patient	Cycle	Date	Blodd product	Specify	Total units	Irradiated

Taken from concomitant therapy dataset.

Table 12.6.4 G-CSF, transfusions or EPO during treatment

	N	%
G-CSF	X	X.X
Platelets transfusions		
Packed red cells transfusions		
Plasma transfusions		
Cryoprecipitates		
Clotting factors		
EPO		

Table 12.6.5 Subsequent therapy

	N	%
Type	X	X.X
Chemotherapy		
...		
Subsequent chemotherapy agents (ATC)		
...		
...		

Table 12.6.6 Time to subsequent therapy or death

	Arm A	Arm B	Parameter	p-value
N				
Events				
Censored				
Time to subsequent therapy or death			Log-Rank: HR (95% CI) :	LR: HR:

Kaplan-Meier plot will be also shown (Figure 12.6.7)

12.7 Safety analysis in special subgroups.

Table 12.7.1 Worst grade 3-4 by patient in special subgroups (Gender)

	Male			Female		
	N	Grade 3-4	%	N	Grade 3-4	%
Thrombocytopenia	X	X	X.X	X	X	X.X
Neutropenia						
ALP						
Total bilirubin						
AST						
ALT						
CPK						
Nausea						
Vomiting						
Fatigue						
Other*						

(*)Any treatment-related toxicity present in >=5% of patients in any group

Table 12.7.2 Worst grade 3-4 by patient in special subgroups (Race)

	White			Other		
	N	Grade 3-4	%	N	Grade 3-4	%
Thrombocytopenia	X	X	X.X	X	X	X.X
Neutropenia						
ALP						
Total bilirubin						
AST						
ALT						
CPK						
Nausea						
Vomiting						
Fatigue						
Other*						

(*)Any treatment-related toxicity present in >=5% of patients in any group

Table 12.7.3 Worst grade 3-4 by patient in special subgroups (Age)

	<65 years old			≥65 years old		
	N	Grade 3-4	%	N	Grade 3-4	%

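### The AE and SAE outputs have no place for grade 5, so an event that causes death is left out of the severe-event rates by term and subgroup

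*SAP*

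**What the plan says.** Protocol 8.5.3 (Death) makes grade 5 a live grade in this trial: "Grade 5 should be used only for events for which there is a causal relationship with" the patient's death. SAP 7.1 describes toxicities by worst NCI-CTCAE grade, so an event that ends at grade 5 is no longer a grade 3 or 4 event.

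The shells in SAP Appendix I are as follows.

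- **Table 12.2.1.1 (summary of AEs).** There are four severe-event rows, all defined as grade 3/4, among them "Any grade 3/4 AE", "Any grade 3/4 treatment-related AE" and "Any grade 3/4 treatment-related SAE". Fatal events have two rows of their own, for all AEs leading to death and for "AEs treatment-related leading to death".
- **Tables 12.2.1.3 to 12.2.1.6 (AEs) and 12.3.1.1 to 12.3.1.4 (SAEs).** The columns run from Grade 1 to Grade 4, followed by All, footnoted as any grade.
- **Listings 12.2.1.7 to 12.2.1.10.** These are restricted to "grade 3-4 adverse events. Worst grade by patient" and the matching listings by cycle and regardless of relationship.
- **Tables 12.7.1 to 12.7.4 (gender, race, age, BMI).** These use the same restriction, for example "Table 12.7.1 Worst grade 3-4 by patient in special subgroups (Gender").

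No AE or SAE shell uses grade ≥3 or grade 3-5.

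**The concern.** A table of severe toxicity is normally read as everything at grade 3 or worse. Here the worst outcome falls outside that count. A fatal infection, for instance, would add to the any-grade column of its row but to no grade column. It would not be in the grade 3-4 listings, and the subgroup tables have no place for an AE at grade 5.

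What is at stake is the accuracy of the severe-event rates by term and by subgroup. They are understated exactly where the event was fatal, and a reader who sums the grade columns will find that they fall short of the total without explanation. Nothing inferential depends on these outputs: the ORR analysis, the sample size and the futility rules do not use them.

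**Working it through.** The plan states no figure here that could be reproduced. The check is to pass a grade 5 record through each shell and then to size the effect.

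**Step 1. Where a grade 5 record lands**

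| Output | Grades shown | Grade 5 term |
|---|---|---|
| Table 12.2.1.1, severe rows | 3/4 | Not counted by that record |
| Table 12.2.1.1, death rows | Fatal AEs | Counted, no term |
| Tables 12.2.1.3-6 and 12.3.1.1-4 | 1 to 4, All | Only under All |
| Listings 12.2.1.7-10 | 3-4 | Absent |
| Tables 12.7.1-4, AE rows | 3-4 | Absent |
| Listing 12.3.1.5 (SAEs) | Not restricted | Listed |
| Table 12.3.2.1, Listings 12.3.2.2-3 | Deaths | Counted or listed |

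In Tables 12.7.1-4, seven of the ten named rows are laboratory parameters (thrombocytopenia, neutropenia, ALP, total bilirubin, AST, ALT, CPK). The point concerns only nausea, vomiting, fatigue and the row for other treatment-related toxicity.

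**Step 2. Made-up records, to see what each counting rule does**

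- Patient 1: term A, grade 5.
- Patient 2: term B, grade 5; term C, grade 3.
- Patient 3: term D, grade 3 and then grade 5.
- Patient 4: term E, grade 4.
- Patient 5: term F, grade 2.

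By patient and term, worst grade ≥3 gives five severe entries: A, B, C, D and E. Worst grade in {3, 4} keeps two (C and E) and loses the three that ended at grade 5.

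For the summary rows the result depends on how the row is read.

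- If any record graded 3 or 4 counts, patients 2, 3 and 4 are counted and only patient 1 is lost. Patient 3 is counted only if the earlier grade 3 is kept as its own record.
- If the patient's worst grade must be 3 or 4, only patient 4 is counted.
- With grade ≥3, patients 1 to 4 are counted.

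The row labels fit the first reading better. The SAP does not state the rule. In the worst-grade outputs the fatal term is lost on either reading.

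**Step 3. Size per affected patient**

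Change in the overall severe-event rate = 1 / (number treated). Safety uses the All Treated Patients set (SAP 4.3), whose size is not fixed.

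- Assumption (a): 60 treated, equal to the planned number of centrally confirmed patients. 1/60 = 1.7 points.
- Assumption (b): the roughly 30% diagnostic discordance cited in Protocol section 3 applies in full. Unconfirmed patients are replaced but stay in the safety set (Protocol 5.3), so the number treated is 60 / 0.70 = 85.7, about 86. 1/86 = 1.2 points.

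**The case against.** The strongest reply is that no fatal event is lost. A fatal AE is serious by definition (Protocol 8.5.2), so it enters SAE Listing 12.3.1.5, which has no grade limit. It is counted under All and in the death rows of Table 12.2.1.1. SAP 7.1 promises AEs with fatal outcome by relationship, Listing 12.3.2.3 gives them by preferred term and grade, and SAP 10.2 asks for an in-depth description of treatment-related deaths. Progression is not an AE (Protocol 8.5.1), so deaths from lymphoma should not create grade 5 records. Showing grade 3/4 apart from deaths is also a common layout, and these are unfilled, descriptive templates.

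Most of that stands, and it limits the point to one of rates. It does not remove it. Table 12.3.2.1 has only three causes of death, and the listings carry no denominators and no subgroups. Adding the death row to a grade 3/4 row does not recover grade ≥3, because one patient can be in both.

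Four stronger readings are tempting, and the documents do not support them.

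- A reader might infer that any patient with a fatal event drops out of the severe-event rows altogether. The summary rows may still count a patient who has another grade 3 or 4 record, and the listings still show that patient's other severe terms.
- A reader might infer that fatal toxicity is concealed. The outputs just named show that it is not.
- A reader might put a total on the understatement by supposing two or three such deaths. The documents give no expected number of fatal AEs, so only the effect per patient can be stated.
- A reader might want to change Protocol 8.5.3 as well, since it also says "Grade 4 should be used for the events with the outcome of death but there is no causal relationship between them". That is a question about how events are graded at collection. It would need a protocol amendment with authority and ethics approval (Protocol 10.1), and the table shells can be corrected without it.

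**Conclusion.** The point holds for the worst-grade AE and SAE tables, the grade 3-4 listings and the AE rows of the subgroup tables: a term that ends at grade 5 is missing from each severe-event count. It holds in part for the summary rows of Table 12.2.1.1, where a patient whose only grade ≥3 event is fatal is not counted, and a patient with another grade 3 or 4 record may still be.

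Each patient in the first group lowers the overall severe-event rate by about 1.2 to 1.7 points, under the assumed range of 86 to 60 treated. The total effect cannot be given. This is a defect of presentation that makes severe-event rates incomplete. It does not hide deaths, and it does not touch the primary endpoint, the error rates or the laboratory-grade tables.

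**What to change.** In SAP Appendix I:

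1. Add a Grade 5 column to Tables 12.2.1.3-12.2.1.6 and 12.3.1.1-12.3.1.4, so that the grade columns add up to All.
2. Replace grade 3/4 and grade 3-4 with grade ≥3 (3-5) in the four severe rows of Table 12.2.1.1, in Listings 12.2.1.7-12.2.1.10, and in the nausea, vomiting, fatigue and other rows of Tables 12.7.1-12.7.4. A footnote can mark that the laboratory rows of those tables are unchanged.
3. State the counting rule for the summary rows: a patient counts once if any AE record is grade 3, 4 or 5.
4. Keep the separate death rows and the deaths outputs as they are.

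The cost is table-shell wording, with no new data and no change to the protocol. The downside is slightly higher severe-event figures. Readers who want grade 3-4 alone can still take it from the Grade 3 and Grade 4 columns of the tables by term.
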